## **Procedures**

### ***1. HDFCCC Essential Regulatory Documents***

#### **Documents Filed in iRIS:**

- UCSF IRB approvals for initial submission of application, all modifications, and continuing annual renewals
- Current and prior approved protocol versions with signed protocol signature page(s)
- UCSF IRB approval letters and Informed Consent Form(s) (ICF)
- Current and prior versions of the Investigator Brochure (IB).
- Serious Adverse Event Reporting
- Protocol Violations and Single Patient Exception (SPE) Reports to the UCSF IRB with supporting fax documentation

#### **Documents Filed in OnCore®:**

- Package Insert (if the study drug is commercial) or Investigator Brochure
- Protocol Review Committee (PRC) approved protocols, protocol amendments and Summary of Changes (SOC)
- Patient handouts
- Screening/enrollment log
- Data and Safety Monitoring Committee (DSMC) monitoring reports
- OnCore® Case Report Form (CRF) completion manual

**Documents Filed in Regulatory Binder:**

- Completed Food and Drug Administration (FDA) 1572 document with Principal Investigator's signature
- For all Principal Investigators and Sub-Investigators listed on the FDA 1572, will need Financial Disclosure Forms, CVs, MD Licenses, Drug Enforcement Agency (DEA) Licenses, and Staff Training Documents (i.e., Collaborative Institute Training Initiative (CITI), etc.)
- Site Initiation Visit (SIV) minutes and correspondence with participating site(s).
- As applicable, approvals for Biosafety Committee, Radiation Committee, and Infusion Center
- Serious Adverse Event (SAE) reports to IRB and sponsor.
- BMS pregnancy reporting forms, if applicable
- MedWatch reporting to FDA and sponsor
- Delegation of Authority Form
- Drug Destruction Standard Operating Procedure (SOP)
- For all laboratories listed on the FDA 1572, will need CLIA certifications, CAP certifications, lab licenses, CVs of Lab Directors, and laboratory reference ranges

***2. Additional Essential Documents for Multicenter Trials for the Coordinating Center (filed in Regulatory Binder or OnCore)***

- Institutional Review Board (IRB) approval letters, IRB roster, Informed Consent Form (ICF), and Health Insurance Portability and Accountability Act (HIPAA) Consent Form for the Participating Site(s)
- For all Principal Investigators and Sub-Investigators listed on the 1572 at the Participating Site(s) – Financial Disclosure Forms, CVs, MD Licenses, and Staff Training documents (i.e. Collaborative Institute Training Initiative (CITI), etc.) (for Investigational New Drug Application)
- Site Initiation Visit (SIV) minutes and correspondence with Participating Site(s).
- As applicable, approvals for Biosafety Committee, Radiation Committee, and Infusion Center for the Participating Site(s)
- Protocol Violations and Single Patient Exception (SPE) reports to IRB with supporting fax documentation for Participating Site(s)
- Drug Destruction Standard Operating Procedure (SOP) for the Participating Site(s)
- Data and Safety Monitoring Committee (DSMC) monitoring reports for the Participating Site(s)
- For all laboratories listed on FDA 1572, will need CLIA certifications, CAP certifications, lab licenses, CVs of Lab Directors, and laboratory reference ranges for the Participating Site(s)
- Copy of the Data and Safety Monitoring Plan (DSMP) Monitoring Plan for all participating site(s) in Multicenter studies or Contract Research Organization (CRO) Monitoring Plan (if an outside CRO is used for the study)
- Serious Adverse Event (SAE) forms submitted to both the IRB and the sponsor for the Participating Site(s)

27 April 2012

**3. Required Regulatory Documents for Sub-sites Participating in a UCSF Investigator Initiated Multicenter Trial (Checklist)**

Directions:

- 1) Fax the documents listed below to the UCSF Coordinating center [REDACTED] or
- 2) Scan the documents and upload to OnCore® and create a Note to File for the on-site Regulatory binder to indicate where these documents may be found

**1572**

PI and Sub investigators:

CV and Medical license  
Financial disclosure form  
NIH or CITI human subject protection training certification

Laboratories

CLIA and CAP  
CV of Lab Director and Lab Licenses  
Laboratory reference ranges

**Local Institutional Review Board**

IRB Approval letter  
 Reviewed/Approved documents

- Protocol version date: \_\_\_\_\_
- Informed consent version date: \_\_\_\_\_
- Investigator Brochure version date: \_\_\_\_\_
- HIPAA

Current IRB Roster

**Other**

Delegation of Authority Log

- Include NIH or CITI human subject protection training certificates or GCP training certification

Pharmacy

- Drug destruction SOP and Policy

Protocol signature page

Executed sub contract

27.apr.2012

## Appendix 4 Specimen and Blood Collection

---

### A. For tissue analysis:

Immunohistochemistry (IHC) analyses will be performed on the following diagnostic biopsy tissue specimens.

1. Baseline biopsy tissue (nasopharyngeal tumor tissue, core biopsy) is required to be submitted. Fresh nasopharyngeal tumor tissue obtained from a biopsy within 90 days prior to C1D1 is preferred but archival blocks of tissue are acceptable.

Acquisition of representative formalin-fixed paraffin-embedded (FFPE) tumor specimens in paraffin blocks (blocks preferred) or at least 15 slides, with an associated pathology report, is required.

Criteria for fresh tissue collection: 1) exophytic mass or tumor, or 2) amenable to cup forceps or ultrasound guided core biopsy. At least three cores should be obtained. A fine needle aspirate is not acceptable.

If tumor may not be able to be obtained from the primary site safely at all initial and subsequent tissue collection timepoints, then tissue from another anatomic area (e.g. core biopsies of neck) should be substituted. Every effort should be made to biopsy at baseline and subsequently from the same tissue site, e.g. always from the primary nasopharyngeal tumor or always from the neck.

2. 1 – 2 further tumor samples should be collected (if deemed appropriate by the investigator) as follows:
  - a) Dose Schedule 1: (1) After the first cycle of nivolumab AND (2) after the first week of radiation therapy.
  - b) Dose Schedule 2 and 3: (1) After the first week of radiation therapy.

See above for specifications of criteria for tissue collection. These samples should be collected from the same site that was biopsied at baseline.

See Laboratory Manual for processing and submission of paraffin-embedded tissue.

Formalin Fixed Paraffin Embedded (FFPE) tissue is stored at room temperature. These tissue samples may be batch-shipped to the UCSF Cancer Immunotherapy Lab for analysis.

### B: For blood analyses:

All patients will have 4 (four) 10mL green top tubes and a purple top EDTA of blood specimens collected at baseline, at cycle 7 day 1 prior to initiation of adjuvant-phase nivolumab (whether nivolumab is actually given or not), and at 1 year followup. The purple top tube of blood will be reserved for EBV DNA testing in addition to immunologic correlative analyses.

Other than these three time points, 4 (four) 10mL green top tubes of blood specimens will be collected on day 1 and before administration of each nivolumab cycle. In addition, 4 (four)

10mL green top tubes of blood specimens will be collected at time of treatment discontinuation, and 4 (four) 10mL green top tubes of blood specimens will be collected at each regular post-treatment follow-up (at 1, 3, 6, 9 months post-treatment).

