### 3.2 Study Schema

#### On-treatment schema (Dose Schedule 1):

		Adjuvant Phase																							
Cycle #	1	2	3		4		5		6		7		8		9		10		11		12				
Week #	1	2	3	4	5	6	7	8	9	10	11	12	13	14	15	16	17	18	19	20	21	22	23		
Cisplatin		C	C	C	C	C	C	C																	
Radiation		X	X	X	X	X	X	X																	
Nivolumab	N	N	N		N	N							N		N		N		N		N		N		

Nivolumab schedule (starting dose schedule): Priming and concurrent nivolumab will be given in conjunction with chemoradiation. Patients will receive 1 cycle of priming nivolumab on C1D1, and 14 days later, start weekly cisplatin 40 mg/m^2, IV, concurrent with 33-35 fractions (6.5-7 weeks) of RT, with concurrent cycles 2-5 of nivolumab every 14 days. No nivolumab will be given on C6D1, to allow for recovery from toxicities. At C7D1, patients will initiate adjuvant nivolumab, every 14 days for cycles 7-12. Immune-related toxicities should be at grade 1 or lower prior to starting a patient on the adjuvant phase of therapy; if not, initiation of the adjuvant phase should be delayed until resolution of toxicities.

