#### On-treatment schema (Dose Schedule 2):

		Adjuvant Phase																							
Cycle #	1	2	3		4		5		6		7		8		9		10		11						
Week #	1	2	3	4	5	6	7	8	9	10	11	12	13	14	15	16	17	18	19	20	21				
Cisplatin	C	C	C	C	C	C	C																		
Radiation	X	X	X	X	X	X	X																		
Nivolumab	N	N	N	N	N	N					N	N		N	N	N	N	N	N	N	N	N	N		

Nivolumab schedule (Dose Schedule 2): Priming and concurrent nivolumab will be given in conjunction with chemoradiation. Patients will receive 1 cycle of nivolumab on C1D1 (no priming), and start weekly cisplatin 40 mg/m^2, IV, concurrent with 33-35 fractions (6.5-7 weeks) of RT, with concurrent cycles 2-5 of nivolumab every 14 days. No nivolumab will be given on C5D1, to allow for recovery from toxicities. At C6D1, patients will initiate adjuvant nivolumab, every 14 days for cycles 6-11. Immune-related toxicities should be at grade 1 or lower prior to starting a patient on the adjuvant phase of therapy; if not, initiation of the adjuvant phase should be delayed until resolution of toxicities.

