a Each 14-day period of treatment will represent 1 cycle and begins from C1D1.b Baseline conditions assessmentc As part of efficacy assessments, quality of life by FACT-NP, FACT-Taxane, HHIE-S, and EuroQOL EQ-5D will be administered at baseline, at cycle 6, at end of treatment and at all followup visits. Survey's not available in the patient's language may be administered by the study staff in an interview format with a translator, however failure to obtain any individual quality of life survey not available in the patient's language will not be considered a protocol deviation.d Toxicity will be assessed by CTCAE v5.0f There is a 72 hour window of scheduled nivolumab administration. **In Dose Schedule 1:** Nivolumab will be administered on C1D1 for priming and then q14 days beginning C2D1, concurrent with chemoradiation, until C5D1. Nivolumab will not be administered on C6D1 to allow for any resolution of toxicities. Beginning C7D1, adjuvant nivolumab q14 days will be administered until C12D1. **In Dose Schedule 2:** Nivolumab will be administered on C1D1 concurrent with chemoradiation (no priming), and then q14 days until C4D1. Nivolumab will not be administered on C5D1 to allow for any resolution of toxicities. Beginning C6D1, adjuvant nivolumab q14 days will be administered until C11D1. **In Dose Schedule 3:** Nivolumab will not be administered until after completion of chemoradiation. Beginning C6D1, adjuvant nivolumab q14 days will be administered until C11D1. Immune-related toxicities should be at grade 1 or lower prior to starting a patient on the adjuvant phase of therapy; if not, initiation of the adjuvant phase should be delayed until resolution of toxicities.h Physical Exam includes weight measurementsi Disease-specific criteria (for CRF purposes, e.g.: GU assessment, BR disease Eval, AML-MDS Summary, etc.)j Measurable disease will be assessed using RECIST 1.1 criteriak For the **baseline** tissue collection, if a biopsy was performed within 90 days prior to C1D1, and no intervening treatment was given, a repeat biopsy is not required if adequate tumor tissue can be provided. **Repeat biopsy** will be at the discretion of the investigator, and timing will depend on Dose Schedule. **In Dose Schedule 1:** Tumor tissue post-nivolumab during cycle 1 AND after first week of radiation therapy. **In Dose Schedule 2 and 3:** Tumor tissue after first week of radiation therapy only. See appendix 4 for further details.l All blood draws may be completed within 7 days prior to start of therapy unless otherwise specified; screening labs must be completed within 14 days of Cycle 1 Day 1.m Hemoglobin, hematocrit, platelets, total white blood cell count (WBC) and differentialn Alkaline phosphatase, aspartate aminotransferase/alanine aminotransferase (ALT/AST), total bilirubin, total protein, albumin, calcium, phosphorus, magnesium, blood urea nitrogen (BUN), creatinine, glucose fasting), potassium, sodium, chloride, bicarbonate, uric acid, LDH, fasting lipid panel (LDL, total cholesterol, triglycerides), thyroid stimulating hormone (TSH).o **Pre-menopausal females:** serum or urine pregnancy test within 7 days prior to start of study drug. Serum pregnancy test by local laboratory  $\leq$  1 day prior to C1D1 for women of childbearing potential. If the serum pregnancy test results are not available on C1D1, a urine pregnancy test can be performed on C1D1 to confirm that the patient is not pregnant prior to dosing.p See Appendix 4 for details on tissue specimen collection and processing.q Collection of peripheral blood for correlative biomarkers and peripheral immune changes must be collected with every cycle of nivolumab. Blood will also be collected in post-treatment followup to 1 year.r Imaging with MRI nasopharynx/face/neck and whole body PET-CT will be performed at screening and at end of treatment and at 1 year followup, with further imaging to be performed as clinically indicated.

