#### 8.1.2 Secondary Endpoints

**Efficacy:** ORR as assessed by the study investigator by RECIST 1.1 criteria. The ORR is defined as the best overall response (BOR) recorded from the first day of treatment until time of assessment.

**Safety and tolerability:** Evaluate the number and frequency of Adverse Events (AEs) as determined by National Cancer Institute Common Toxicity Criteria (NCI-CTC) version 4.0 by investigator assessment.

- To determine the clinical response as judged by the investigator;
- To determine the overall response rate from the first day of treatment to 1 year post-treatment, as determined by RECIST 1.1 criteria;
- To determine the locoregional control rate at 1 year post-treatment;
- To determine the distant metastasis rate at 1 year post-treatment;
- ;
- To determine the rate of EBV DNA clearance at end of chemoradiation and at 1 year post-treatment;  
To determine the acute and late toxicity rates according to CTCAE v5.0, including immune-related adverse events (AEs);
- To assess patients' quality of life from baseline through 1 year post-treatment;

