	# of green + purple top tubes
Baseline or before treatment on C1D1	4 (40mL total) + 1 (10mL total)
Day 1 of each cycle (before administration of study therapies)	4 (40mL total)
Day 1 of cycle 7	4 (40mL total) + 1 (10 mL total)
Treatment discontinuation	4 (40mL total)
Follow-up at 1, 3, 6, 9 months post-treatment	4 (40mL total)
Follow-up at 12 months post-treatment	4 (40mL total) + 1 (10 mL total)

See Laboratory Manual for processing and submission of blood samples.

Blood samples should be stored at room temperature no longer than 24 hours.

Peripheral blood mononuclear cells (PBMCs) and plasma should be isolated within 24 hours of blood collection and stored at -80°C. These samples may be batch-shipped to the UCSF Cancer Immunotherapy Lab for analysis.

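### If the run-in moves to Dose Schedule 2 or 3, the only EBV DNA tube designated between baseline and 1 year (C7D1) falls after the planned start of adjuvant nivolumab

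*Combined protocol and SAP*

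**What the plan says.** Appendix 4, part B, has every patient give a purple-top tube at three times: baseline, 1-year follow-up and, in between, "at cycle 7 day 1 prior to initiation of adjuvant-phase nivolumab". On its use it says: "The purple top tube of blood will be reserved for EBV DNA testing in addition to immunologic correlative analyses". At the other treatment cycles the text lists green-top tubes only: "4 (four) 10mL green top tubes of blood specimens will be collected on day 1 and before administration of each nivolumab cycle". The tube table that follows labels the middle purple-top row simply "Day 1 of cycle 7". Neither the text nor the table separates the dose schedules, although part A of the same appendix does so for tissue.

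The schemas in Section 3.2 start the adjuvant phase at different cycles. For Dose Schedule 1: "At C7D1, patients will initiate adjuvant nivolumab, every 14 days for cycles 7-12". For Dose Schedule 2: "At C6D1, patients will initiate adjuvant nivolumab, every 14 days for cycles 6-11". Schedule 3 carries the same sentence as Schedule 2. Table 6.1, footnote f, agrees for both: "Beginning C6D1, adjuvant nivolumab q14 days will be administered until C11D1".

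The endpoint concerned is listed in Section 8.1.2: "To determine the rate of EBV DNA clearance at end of chemoradiation and at 1 year post-treatment". It also appears in the Abstract and in Section 2.2.

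**The concern.** The blood section appears to have kept Schedule 1 cycle numbers after the two fallback schedules were defined. In Schedules 2 and 3 the instruction contradicts itself: C7D1 is the planned day of the second adjuvant dose, so a draw there does not precede adjuvant treatment. A site working from the tube table would see only the cycle number.

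The purpose of an end-of-chemoradiation reading is to record EBV DNA status before the adjuvant phase acts on it. Section 1.4.2 gives post-radiation plasma EBV DNA more prognostic weight than the pre-treatment level, so the timing is not incidental. Schedule 3 shows the problem most clearly. Those patients have no nivolumab before C6D1, so a pre-dose C6D1 sample would reflect chemoradiation alone, whereas a C7D1 sample follows their first nivolumab dose.

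**Working it through.** The plan states no figure for this interval, so the check is calendar arithmetic.

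**Inputs**
- Cycle length is 14 days, counted from C1D1 (Section 6.1.2; Table 6.1, footnote a).
- Radiation is 33-35 fractions (Section 3.2), given 5 per week (Section 5.1.1.1, Dose Specifications).
- Chemoradiation starts 14 days after C1D1 in Schedule 1, that is at C2D1, and at C1D1 in Schedules 2 and 3 (Section 3.2).
- Adjuvant nivolumab starts at C7D1 in Schedule 1 and at C6D1 in Schedules 2 and 3 (Section 3.2; Table 6.1, footnote f).
- Assumptions: radiation starts on a Monday, there are no delays, and cycle numbers follow the calendar.

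**Day of CnD1** = 1 + 14 × (n − 1). So C2D1 = day 15, C6D1 = 1 + 14 × 5 = day 71, and C7D1 = 1 + 14 × 6 = day 85.

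**Last radiation day.** Thirty fractions fill six weeks. Fraction 33 therefore falls 6 × 7 + 2 = 44 days after the first, and fraction 35 falls 6 × 7 + 4 = 46 days after it.
- Schedule 1: 15 + 44 = day 59, to 15 + 46 = day 61.
- Schedules 2 and 3: 1 + 44 = day 45, to 1 + 46 = day 47.

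**Consistency check.** Day 85 is the first day of week 13 and day 71 the first day of week 11. These match the adjuvant start weeks drawn in the Schedule 1 and Schedule 2 schemas.

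| | Schedule 1 | Schedules 2 and 3 |
|---|---|---|
| Radiation ends | day 59-61 | day 45-47 |
| First adjuvant dose | day 85 (C7D1) | day 71 (C6D1) |
| EBV DNA tube as tabulated | day 85 | day 85 |
| Days from radiation end to tube | 24-26 | 38-40 |
| Adjuvant doses before tube | 0 | 1, given 14 days earlier |
| Days from radiation end to first adjuvant dose | 24-26 | 24-26 |

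**Sensitivity**
- The ±3-day visit window in Table 6.1 does not close the gap. With C6D1 three days late and C7D1 three days early, the tube is still 14 − 6 = 8 days after the first adjuvant dose.
- The Abstract puts the adjuvant start 4 weeks after chemoradiation, or later if toxicity has not resolved. Counting 28 days from radiation end in Schedules 2 and 3 gives day 73-75 (45 + 28 to 47 + 28), which is still 10-12 days before day 85.
- On the calendar numbering assumed here, C7D1 comes no later than the first adjuvant dose only if that dose slips by a full cycle (14 days) or more.

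**After the correction.** If the tube is tied to the pre-dose visit of the first planned adjuvant cycle, the last row of the table applies: 24-26 days after radiation and no earlier adjuvant dose, in all three schedules.

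**Is there another EBV DNA tube?** Sections 6.1.2.1, 6.1.3 and 6.1.4 mention blood for EBV DNA during treatment, at end of treatment and at follow-up, but refer to the schedule for timing. The blood row of Table 6.1 and its footnote q do not name an EBV DNA time point. Appendix 4 gives purple-top tubes only at baseline, C7D1 and 12 months.

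**The case against.** Several points on the other side have force.

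- **The problem is contingent.** Schedule 1 is the starting schedule and its C7D1 draw is consistent. Under Section 8.2.2 the run-in moves on only if 3 or more of 6 patients have grade 3-4 immune-related toxicity or another DLT. This stands.
- **The stated intent points the right way.** A site that follows the words rather than the cycle number would draw before the first adjuvant dose. This stands for the text, but the tube table carries only the cycle number.
- **The link to the endpoint is inferred.** No section labels the C7D1 tube as the end-of-chemoradiation sample, and the Laboratory Manual is not part of these documents. The inference is reasonable because no other purple-top tube falls between baseline and 1 year.
- **The sample may not be lost.** A reader might infer that a missed draw leaves nothing to test. The documents do not support that. Green-top blood is planned before dosing on day 1 of each cycle, plasma is to be isolated and frozen, and excess material is banked. Pre-dose C6D1 plasma may therefore be in store. The plan does not assign it to EBV DNA, and its suitability for the assay cannot be judged from here.
- **The direction of bias is not known.** A reader might infer that a later draw overstates clearance. Section 1.4.2 reports that EBV DNA can rise 3 to 7 months before clinical recurrence, so a later draw could also turn positive. In Schedules 1 and 2 concurrent nivolumab has been given before any such draw, so even a correctly timed sample would not isolate chemoradiation.
- **Comparison across schedules carries little weight.** A reader might infer that a planned comparison is spoiled. None is planned for efficacy, the primary analysis is confined to the selected schedule, and an abandoned schedule contributes only 6 run-in patients.

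**Conclusion.** The inconsistency is real and conditional. If the run-in moves to Schedule 2 or 3, Appendix 4 contradicts Section 3.2 and Table 6.1. Absent a delay, a C7D1 draw then falls on the second adjuvant dose day, 14 days later relative to radiation than in Schedule 1. No tube designated for EBV DNA is then drawn between chemoradiation and the adjuvant start. Every patient at that schedule sampled by the tube table and without such a delay would be affected, and one named secondary endpoint would mix chemoradiation and adjuvant effects.

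This rests on calendar cycle numbering, a Monday start, no treatment delay, and the inference that the C7D1 tube is the end-of-chemoradiation sample. It does not touch the primary endpoint, and Schedule 1 needs no change. The documents do not support saying that clearance would be overstated, that the information would be irrecoverable, or that a planned cross-schedule comparison would fail. A correction is worth making before any move to Schedule 2 or 3, because it costs little and removes an instruction that cannot be followed as written without a delay.

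**What to change.** In Appendix 4, part B, replace the C7D1 time point in both the text and the tube table with: *day 1 of the first planned adjuvant cycle, before nivolumab (C7D1 in Schedule 1; C6D1 in Schedules 2 and 3), regardless of whether that dose is then given*. Keep the present rule that the tube is drawn even when the dose is withheld, so that patients who never start adjuvant treatment still contribute a reading.

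In the same amendment, state that this tube is the end-of-chemoradiation sample for the EBV DNA clearance endpoint, so that the link no longer has to be inferred.

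The cost is wording only. The purple-top tube moves to a cycle visit that already has a blood draw in Schedules 2 and 3. The number of tubes is the same, no visit is added and treatment does not change.
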